9.2 Setting

9.2.1 Source Population

This will be a multisite study across several hospitals in European countries in which <<COVID-19 vaccine product>> is approved and recommended for use. The source population for the study will comprise individuals eligible to receive COVID-19 vaccination, considering the product-specific indications and availability of the vaccine, and residing in the catchment areas of participating hospitals. If the COVID-19 vaccine is indicated for a given population, but because of a vaccine shortage is only administered in a more restricted population, the source population will be limited accordingly.

9.2.2 Study Period

9.2.2.1 Self-controlled Risk Interval Design

A guiding principle for defining the study period for the SCRI design is that a full history of timing of both events and exposures must be available throughout the study period [3]. The study period will begin in each hospital when the vaccine becomes available in the catchment area for the hospital and will end on the last date on which data on vaccinations and hospital discharges is available.

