9.2.5.1 Outcome Assessment

In this section, the operational definitions for identifying <<adverse event>> in electronic data should be described, with reference to code lists included in a separate protocol appendix.

[Outcome definitions for the proposed adverse events, including code lists, are currently being developed by another workgroup in this project and will be incorporated in this protocol when they become available.]

<<Adverse event>> will be identified in each participating hospital's discharge database or other electronic data bases using diagnosis codes, or a combination of diagnosis with

procedure or treatment codes in the inpatient, emergency department, or ambulatory speciality care settings. Additionally, electronic laboratory data could be used to identify events, if applicable to the outcome.

For recurrent events in the SCRI design, “washout periods” anchored on the outcome date will be used to identify incident events when multiple visits or codes for the same event occur during follow-up; any events with another event (in any care setting, including inpatient, emergency room, hospital outpatient, or primary care) within the washout period will be excluded. For recurrent events in the case-cross over and vaccinated case-coverage designs, only the first event observed during the study period will be included.

Case validation will be undertaken by clinical reviewers blinded to vaccination status and timing of the event relative to vaccination. Case status and date of outcome onset will be confirmed using medical records, physician questionnaire, or other official documentation (e.g., clinical case notes), depending on the data source. Case status will be determined based on Brighton Collaboration definitions where available [2]. SPEAC is developing a toolbox for case definitions that can be obtained on the Brighton Collaboration website or through the following e-mail address: [contact]. The comparative analysis will only include confirmed cases and the dates of onset assigned by the clinical reviewers.

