Annex 5. Feasibility Questionnaire

General Questions

1. Name of data source: _____
2. Contact person: _____
Institution: _____
E-mail address: _____
Phone number: _____

Outcomes

3. Does your site have a hospital discharge database that captures diagnoses and procedures?
___ Yes
___ No → Stop, thank you for your time
4. Does your site distinguish primary diagnoses from the other diagnoses?
___ Yes
___ No
5. Number of patients treated by your hospital annually:

6. Number of patients treated by your hospital annually for the following outcomes:
 - a. [Outcome A]: _____
 - b. [Outcome B]: _____
 - c. etc
7. What is the geographic area covered in the catchment area for your hospital?

8. What is the population coverage of your hospital?

9. How often are your hospitalisation data refreshed and made available for research?

10. How long is the data lag of the hospitalisation records, that is, how much time passes after hospitalisation before the data are available for research purposes?

11. What is the earliest date of data captured by your hospitalisation data?

12. Are the calendar dates of the hospitalisation available?

Yes, the admission and discharge date are available

Yes, the diagnosis date is available

Yes, other. Please specify: _____

13. Can your site identify diagnoses made in the hospital setting of the following outcomes?

a. [Outcome A]? Yes No

b. [Outcome B]? Yes No Etc.

14. What coding system does your site use for diagnosis in the hospital setting?

15. Does your site have the ability to validate outcomes and dates of outcome onset through the use of medical record review, physician questionnaires, case notes, or other methods?

Yes

No

16. What method can you use to validate outcomes and date of onset?

Medical record review

Physician questionnaire

Case notes

Other, please specify: _____

Exposure

17. Can your site identify receipt of COVID-19 vaccines through linkage with other data?

Yes

No → Stop, thank you for your time.

Note that for this study, primary data collection or other self-report information on vaccinations is not acceptable.

18. To what type of exposure data does your site have access (check all that apply)?

Vaccine registry

Primary care records

Pharmacy dispensing data

Patient vaccination cards

Hospital-based medical records

Other, please specify: _____

19. What is the population coverage of the vaccination data source?

20. What is the geographic area covered by the vaccination data source?

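### The SCRI study period ends at the last discharge-data date with no allowance for the lag from onset to record, so late control-window events can be missed and early incidence rate ratios biased upward

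*Protocol*

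**What the plan says.** Protocol section 9.2.2.1 first states the governing principle: "a full history of timing of both events and exposures must be available throughout the study period". The next sentence fixes the end of the SCRI period, which "will end on the last date on which data on vaccinations and hospital discharges is available". This is firm wording, not a bracketed blank for the investigator.

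Section 9.2.5.1 says that adverse events "will be identified in each participating hospital's discharge database or other electronic data bases using diagnosis codes", alone or combined with "procedure or treatment codes in the inpatient, emergency department, or ambulatory speciality care settings". The comparative analysis uses the "dates of onset assigned by the clinical reviewers", so an event's place in the risk or control window depends on onset, not on discharge.

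Three other places bear on completeness. Section 9.1 says that the SCRI includes a case only when both intervals have accrued. Annex 3 says that data must have accrued to the end of follow-up for each dose, and it treats outcome data over the whole of both intervals as a key assumption. The inclusion criteria in section 9.2.3.1 do not repeat any of this.

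On lag, section 9.3 asks that it be described for each data source. Annex 5 question 10 asks sites "how much time passes after hospitalisation before the data are available for research purposes". No section uses the answer to set the end of the study period.

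**The concern.** An inpatient with onset 10 days before the end date and a 25-day stay has an onset inside the study period but no discharge record in it. Every such patient is missing from a discharge-based search, so the event history is incomplete just before the end date, contrary to the section's own principle.

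The loss is not balanced. With a postvaccination control window, control time always lies closer to the end date than risk time for the same dose. Losing control events raises the IRR when the vaccine has no effect.

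The consequence is greatest when most included doses are recent, which is the position in an early report. Section 9.1 (Table 2) makes the SCRI the only listed analysis when temporal trends in vaccination are suspected and cannot be adjusted for, and Annex 3 recommends the design for timely results. An upward bias there could look like a safety signal.

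**Working it through.** **Plan's own figure.** There is none for lag, length of stay or the resulting bias. The only SCRI figures are the sample sizes in Table 3. All 15 reproduce with the signed-root-likelihood formula at an assumed two-sided 0.05 level, and they are unaffected by this point.

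**Inputs from the protocol.** Windows of Figure 3-1: risk days 1–42, control days 51–92. Each is 42 days wide, and their starts are 50 days apart. The accrual rule is applied: a dose counts only if its day 92 has been reached by the end date.

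**Assumptions, not in the documents.** True IRR 1; vaccinations evenly spread from day 0; every case seen only after an exponential onset-to-record lag with mean L days. If the end date is the last discharge held, L covers onset to discharge. If it is the extraction date, L also covers coding and release.

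**Formula.** Let D be days of data and K = D − 92, the span of vaccination dates that qualify.

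- Share of control events missed: c = [L(1 − e^(−K/L))/K] × [L(1 − e^(−42/L))/42]
- Share of risk events missed: r = c × e^(−50/L)
- Null IRR = (1 − r)/(1 − c)

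**Worked case, L = 20, D = 180 (K = 88).** c = [20 × 0.9877/88] × [20 × 0.8775/42] = 0.2245 × 0.4179 = 0.0938. r = 0.0938 × 0.0821 = 0.0077. Null IRR = 0.9923/0.9062 = 1.095.

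| Mean lag L (days) | D = 180 | D = 270 | D = 365 |
|---|---|---|---|
| 5 | 1.007 | 1.003 | 1.002 |
| 10 | 1.027 | 1.013 | 1.009 |
| 20 | 1.095 | 1.045 | 1.029 |
| 30 | 1.171 | 1.081 | 1.051 |

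Summing day by day instead moves the two largest entries at 180 days only within 1.09–1.10 and 1.17–1.18, depending on how part-days are counted.

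**Very early report.** With K = 30 and L = 5, 10 and 20, the formula gives 1.02, 1.08 and 1.25. Day-by-day sums for the other example windows in section 9.2.5.3 give 1.01, 1.04 and 1.13 (1–42 against 43–127) and 1.08, 1.16 and 1.25 (0–7 against 8–15).

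**Sensitivity.** If half the cases are found without waiting for discharge, c and r halve. The L = 20, D = 180 value becomes (1 − 0.0039)/(1 − 0.0469) = 1.05, and the very early values fall to about 1.01–1.11. If uptake grows 3% per day, the very early values become about 1.01–1.30. With K = 180 and L = 20, such growth gives 1.18 instead of 1.05.

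**Effect of an earlier end date.** Moving the end back by B days multiplies c by e^(−B/L) and replaces K by K − B. For L = 20, D = 180 and B = 60 (about the 95th percentile of an exponential lag, which is 3.0 × L): c = 0.0498 × [20 × 0.7534/28] × 0.4179 = 0.0112, r = 0.0009, and the null IRR is 1.01. For L = 30 and B = 90, no dose qualifies at 180 days (K − B = −2); at 270 days the null IRR is 1.01.

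**The case against.** The strongest answer is that the protocol already requires what is asked. The full-history principle stands directly before the end-date sentence. Annex 3 speaks of data accruing, not merely of time passing, and makes complete outcome data over both intervals a key assumption. A careful reader could take the last date of available data to mean the last date through which events are complete. What stands is that these rules exclude doses whose control window is still open. What they do not do is say that accrual includes time to discharge and coding, and a site that follows the end-date sentence literally would not wait for it.

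Second, cases need not come from discharge records. Section 9.2.5.1 admits a "discharge database or other electronic data bases using diagnosis codes", covers emergency and ambulatory care, and allows laboratory data. Through those routes discharge lag matters little. This stands and limits the reach of the point, although Annex 5 ends the questionnaire for a site that answers no to "Does your site have a hospital discharge database that captures diagnoses and procedures".

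Third, this is a template, and a cut-off specific to a site and outcome is normally set later. That is fair for the number of days. It does not excuse an end-date rule that conflicts with the principle beside it.

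Fourth, early SCRI results are not the main route: section 9.1 prefers the other two designs for timeliness, Table 2 makes the SCRI primary in one of four scenarios, and the interim reports are placeholders. Missed cases also appear at the next data refresh. This bears on importance, not on direction.

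**Conclusion.** The end-date rule in section 9.2.2.1 can breach the section's own full-history principle, and it should be reworded. Where cases are found mainly through discharge records, the bias is upward. Its size depends wholly on assumed lags, even uptake and the Figure 3-1 windows: negligible to about 3% for mean lags of 10 days or less with at least 180 days of data; about 10% to 18% for mean lags of 20 to 30 days with 180 days of data; more in very early reports; about 5% or less by one year. Rising uptake enlarges these figures, and case finding outside discharge records reduces them.

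A reader might infer more than this, in three ways that the documents do not support:

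- **That every SCRI estimate under this protocol is inflated.** No length of stay, record lag or uptake rate is given, and other case sources are allowed.
- **That control windows are simply cut short by the end date.** Without the accrual rule and without a person-time correction, an early null IRR would be about 1.3–2.5, but section 9.1 and Annex 3 rule that out.
- **That the risk window is always complete.** In the 0–7 against 8–15 day example, a 20-day mean lag and K = 30 lose about 29% of risk events and 43% of control events. The bias comes from the difference.

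**What to change.** In section 9.2.2.1, end the SCRI study period, for each site and outcome, at the date through which onset-dated events are essentially completely captured: the last data date minus the site's onset-to-record lag for that outcome. Sites that identify cases by admission, emergency or ambulatory records may use the date to which those records are complete. In section 9.2.3.1, state that a dose is included only if its control window ends by that date, so that the accrual rule appears among the inclusion criteria.

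The lag should come from the site's own length-of-stay and data-lag information. Annex 5 question 10 is not enough alone: it asks about time after hospitalisation, and the questionnaire does not ask for length of stay, so one question on onset or admission to discharge should be added. The percentile that counts as essentially complete is a choice to be stated; the 95th was used above only as an illustration.

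The cost is a sentence in each of the two sections, one added question and one parameter per site and outcome. The downside is delay: the most recent vaccinations enter at a later data refresh, and with a long lag an early SCRI report may have no eligible doses.

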9.2.2.2 Case-Crossover and Vaccinated Case-Coverage Designs

For the CCO and vaccinated case-coverage designs, a full history of timing of exposures must be available in the risk and comparison windows preceding captured events. Therefore, the study period should comprise a period during which data on both exposures and outcomes are available.

For the CCO study, the study period should be selected to cover a time frame during which the propensity to receive the vaccine is relatively constant over time in the source population. If a such a study period is not available, the CCO design should not be used.

9.2.3 Study Population and Follow-up Period

This section should explicitly describe the study population and follow-up periods for the SCRI, CCO, and vaccinated case-coverage designs.

9.2.3.1 Self-controlled Risk Interval Design

To be included in the SCRI, individuals must meet the following criteria. Note that the study population for analysis of each outcome of interest will be different.

- Meets criteria for source population, assessed at the time of vaccination
- Received <<COVID-19 vaccine product>> during the study period
- Must have experienced an event meeting case-identification criteria within the risk or control intervals following vaccination

The follow-up period will begin at the date of vaccination and finish at the end of the control window.

9.2.3.2 Case-Crossover and Vaccinated Case-Coverage Designs

To be included as a case in the CCO or vaccinated case-coverage study, individuals must meet the following criteria. Note that the study population for analysis of each outcome of interest will be different.

- Meets criteria for the source population, assessed at the time of the event
- At least one occurrence of an event meeting case-identification criteria during the study period
- Data on exposures available through the beginning of comparison window

[figure not shown]
The follow-up period will begin at the start of the comparison window (that precedes the exposure window) and will finish at the date of outcome onset.

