If multiple doses are given during the study, the comparison window should be selected such that the underlying propensity to be vaccinated is not correlated between the exposure and comparison window. This guidance is given because individuals who are vaccinated in both windows do not contribute to the analysis and excluding a large number of individuals due to this reason reduces statistical power and precision of risk estimates. As an example, suppose the vaccine dosing schedule calls for two doses approximately 28 days apart, and the risk window is 1 to 21 days prior to the event. If one were to select a control window of 22 to 42 days, we anticipate that many persons would be vaccinated in both windows and become uninformative to the study. To avoid this, the comparison window could be defined as 50 to 70 days before the event; the comparison window could be placed even further before the event to incorporate a washout period between the exposure and comparison window, as needed.

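### The case-crossover inclusion criteria do not require the comparison window to fall after local vaccine availability or inside the constant-propensity period, so events early in that period can push the null odds ratio above 1

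*Protocol*

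**What the plan says.** Section 9.2.3.2 of the protocol sets three inclusion criteria for CCO and vaccinated case-coverage cases. The first is "Meets criteria for the source population, assessed at the time of the event". The second is at least one qualifying event in the study period. The third is "Data on exposures available through the beginning of comparison window".

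Section 9.2.1 defines the population that the first criterion points to: "The source population for the study will comprise individuals eligible to receive COVID-19 vaccination", taking account of indication and availability. It adds that where a product is indicated for a group but "because of a vaccine shortage is only administered in a more restricted population, the source population will be limited accordingly". Membership can therefore change over calendar time.

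For the CCO, section 9.2.2.2 adds that "the study period should be selected to cover a time frame during which the propensity to receive the vaccine is relatively constant over time", and then: "If a such a study period is not available, the CCO design should not be used". Table 1 marks the CCO as unsuitable when vaccination trends are present. Table 2 makes it primary only when trends are not observed, or are not suspected and cannot be checked.

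Section 9.2.5.3 gives an example for a two-dose schedule with an exposure window of 1 to 21 days before the event, in which "the comparison window could be defined as 50 to 70 days before the event".

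**The concern.** Eligibility is tested on one day, the event date, while the CCO contrast reaches back to the start of the comparison window (70 days in the example). A correct record of no vaccination, from a time when vaccination was impossible, satisfies the third criterion.

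The constant-propensity rule applies to the study period, and the second criterion places only the event in that period. An event on day 10 of a well-chosen period has its example comparison window 60 to 40 days before the period begins. If the product was not yet offered to that person's group, the case can count as exposed in the exposure window but never in the comparison window. Section 9.2.2.1 starts the SCRI study period at local availability; section 9.2.2.2 sets no such start for the CCO.

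At stake is a false safety signal from a criterion that a template will pass on to many sites and outcomes.

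**Working it through.** The protocol gives no figure for CCO bias, so there is none to reproduce. Table 3 sizes the SCRI only and is not used as a yardstick.

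**Inputs from the protocol:** example windows of 1–21 and 50–70 days before the event (9.2.5.3).

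**Assumptions:** a single dose; no vaccine effect; a constant daily hazard *h* of vaccination from the day a person becomes eligible; groups opening uniformly over a rollout of *T* days; events uniform over the same *T* days among those eligible.

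**Step 1, one case.** For a person eligible for *E* days before the event, the probability of vaccination *x* days before the event is f(x) = h(1−h)^(E−x) if x ≤ E, and 0 otherwise. With one dose, each informative case is exposed in exactly one window, so

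null OR = Σf(x) over x = 1..21 ÷ Σf(x) over x = 50..70.

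- E < 50: the denominator is 0, so the case can only be discordant towards exposure.
- E = 60: 11 of the 21 comparison days are open. Without depletion the ratio is 21/11 = 1.91; with depletion it is 1.83 (h = 0.001), 1.23 (h = 0.01) and 0.79 (h = 0.02).
- E ≥ 70: each exposure day *x* pairs with day *x* + 49, so the ratio is (1−h)^49, which is 0.95, 0.61 and 0.37 at h = 0.001, 0.01 and 0.02 (0.38 for the last with the continuous form exp(−49h)).

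**Step 2, the criteria as written.** Over the rollout, the number of cases with *E* days of eligibility is proportional to T − E + 1. Summing numerator and denominator with these weights:

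| T (days) | h = 0.001 | h = 0.01 | h = 0.02 |
|---|---|---|---|
| 180 | 1.936 | 1.731 | 1.607 |
| 270 | 1.493 | 1.358 | 1.298 |
| 365 | 1.325 | 1.223 | 1.190 |

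**Step 3, comparison window wholly after first local availability.** Keeping only events on day 70 or later of the rollout:

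| T (days) | h = 0.001 | h = 0.01 | h = 0.02 |
|---|---|---|---|
| 180 | 1.707 | 1.463 | 1.302 |
| 270 | 1.414 | 1.246 | 1.154 |
| 365 | 1.286 | 1.157 | 1.099 |

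Every cell moves towards 1, and none reaches it.

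**Step 4, each person also eligible for the whole comparison window.** All kept cases have E ≥ 70, so the null OR is (1−h)^49 from Step 1, at or below 0.95. The inflation is gone, but depletion of the unvaccinated now biases the OR downward.

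**Step 5, close short windows.** Section 9.1 allows, under observed trends, a control window close to a short exposure window. Assume 1–7 against 8–14 days, h between 0.001 and 0.01, a share of cases newly eligible (1–13 days before the event) and the rest eligible for 60 days. The null OR is 1.02–1.05 with a 10% share, 1.21–1.25 with 30% and 1.45–1.56 with 50%. Closeness does not remove the inflation from newly eligible cases.

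**The case against.** The strongest reply is that a phased rollout is exactly what the protocol calls a temporal trend. Section 9.1 names changing availability and recommendations as a major threat to the CCO. Table 1 rules the design out under trends, Table 2 moves to vaccinated case-coverage or the SCRI, and section 9.2.2.2 withdraws the CCO if no constant-propensity period exists. Sections 9.8 and Annex 3 repeat the limitation. This stands: much of the bias is prevented by design selection, if sites apply it well. A reader might infer that the bias persists in a true no-trend setting. The documents do not support that, since a step from zero to a constant rate is itself a trend.

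It can also be argued that follow-up starts at the comparison window, so that window is meant to lie inside the study period. That reading is reasonable, but the criteria do not state it; only the event is placed there.

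Two further inferences fail:

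- Not every newly eligible case raises the OR. One vaccinated between the two windows, or never, is uninformative. If 10% of cases are newly eligible (1–69 days before the event) and the rest have been eligible for 120 days, the null OR is 1.03 at h = 0.001 and 0.72 at h = 0.01. With 30% it is 1.25 and 1.01.
- Requiring eligibility throughout does not restore an OR of 1.00. That result appears only if depletion is ignored.

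Finally, days 50 to 70 are an example and the document is a template, so the figures are illustrative.

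**Conclusion.** The gap is real but narrower than a general claim that the CCO is inflated. The population-level guard has no counterpart in the case criteria: nothing places the comparison window after local availability or inside the constant-propensity period. Where early events are admitted, the null OR is about 1.2 to 1.95 under uniform rollouts of 180 to 365 days, hazards of 0.001 to 0.02 per day and the example windows. Rollout length, uptake and windows other than the example are unknown, and the size depends on all three. The direction is upward in these rollouts; it can be nil or downward when uptake is fast or newly eligible cases are few.

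Separately, section 9.1's allowance for a close control window under observed trends does not fit Table 1 or section 9.2.2.2, both of which exclude the CCO there.

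Vaccinated case-coverage shares the same criteria but is not affected in the same way, because its calendar-matched reference strata handle the trend.

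**What to change.** 1. In section 9.2.3.2, for the CCO only, state that the whole span from the first day of the comparison window to the event must lie within the constant-propensity study period, and after the product became available to the case's age or risk group in the catchment area. Each site lists the local opening dates.
2. Report results with and without the restriction to people eligible for the whole comparison window. Say that it can bias the OR downward, and do not present it as restoring an OR of 1.
3. Reconcile the close-window option in section 9.1 with Table 1 and section 9.2.2.2.
4. Leave the vaccinated case-coverage criteria as they are.

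The cost is one sentence, a table of dates per site and one additional analysis. Cases from the first weeks of availability are lost. Where the comparison window wholly predates availability, those cases offer no valid within-person contrast.
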